The OPRC program is comprised of representatives from the NICHD (Bethesda, MD) and three Clinical Sites: Northwestern University (Chicago, IL), University of Texas Medical Branch (Galveston, TX) and Magee-Womens Hospital (Pittsburgh, PA). Two other sites, The University of Texas at Houston and the University of Utah, were added as additional sites; however, each site is conducting the study under separate INDs. The research is overseen by an internal Steering Committee, an external Data Monitoring Committee (DMC), the local Institutional Review Boards (IRBs) of each clinical site and the FDA. Details regarding the composition and responsibilities of the Steering Committee and OPRC locations are provided in the Network Policy Manual. Details regarding the composition and responsibilities of the DMC are provided in its charter.

C.2. Primary and Secondary Objectives

We will recruit 300 pregnant women with one or more prior preterm births. **Recruitment will occur at the three OPRC clinical sites and the two additional sites.** Ideally, each center will enroll approximately 100 subjects; however, enrollment may differ substantially between centers. Enrolled subjects will be randomized in a 2:1 ratio to receive a single weekly injection of 500 mg or 250 mg 17-OHPC. The 500 mg dose can be administered either as a single 2 ml weekly injection (500 mg) or two 1 ml (250 mg) weekly injections administered at the same time. Those assigned to the 250 mg weekly dose will receive 1 ml of 250 mg of 17-OHPC.

The Primary Objective of this study is to determine whether the rate of preterm birth is related to the plasma concentration of 17-OHPC.

Secondary Research Questions include the following:

1. What is the impact of race or BMI on plasma 17-OHPC concentrations?
2. Are maternal side effects increased at higher doses or higher plasma concentrations of 17-OHPC?
3. Is there an increase in adverse fetal effects from a higher dose or higher concentrations of 17-OHPC?
4. What is the relationship between dose of 17-OHPC and plasma concentrations?

5. Do single nucleotide polymorphisms in the maternal progesterone receptor, P-glycoprotein affect efficacy or the placental transfer of 17-OHPC?
6. Is efficacy of 17-OHPC affected by the gestational age at therapy initiation, the number of prior PTBs or the gestational age at delivery of prior PTBs?
7. What is the relationship between cord blood concentrations of 17-OHPC and maternal plasma concentrations?

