1. Between 26-30 weeks - but only after a minimum of 7 injections have been administered (1 tube of 7 ml will be drawn just prior to the next injection; this will be a trough level)
2. Between 6-9 weeks after the 26-30 week specimen but not later than 37 weeks (1 tube of 7 ml will be drawn just prior to the next injection; this will be a trough level)

A second tube of blood (7 mL) will be drawn with any of the first 2 blood draws for genotyping of various genes related to preterm birth if mother consents to this optional test.

C.7. Patient Management

No attempt will be made to alter or mandate clinical management of the subjects.

C.7.i Criteria for Stopping Treatment

In the event that either of the two scenarios below occur, treatment with 17-OHPC will stop and the subject will be retained in the study but their data related to 17-OHPC concentration will not be utilized since they will have stopped the medication. Additional subjects will be recruited to maintain the sample size.

- a. Systemic drug allergy, thrombosis during pregnancy, cholestatic jaundice, suicidal ideation, or other concern regarding the patient's safety
- b. Pregnancy termination (not planned at the time of eligibility determination)

The ancillary cohort is an observational cohort. This section is not applicable to the ancillary cohort, as the 17-OHPC medication is prescribed and managed by the subject's healthcare provider.

C.7.ii Non-Compliant Subjects

Compliance with drug administration will be documented by discussion with the subject during the weekly contact with the subject and by counting the used vials. Non-compliant subjects will be retained in the study and treatment with the randomized dose of 17-OHPC will continue; however, their data related to 17-OHPC concentration will not be utilized for the primary outcome. Additional subjects will be recruited to maintain the sample size. Non-compliance will be defined as:

- a. Subjects who miss any injections in the 4 weeks preceding the 26-30 week blood draw.
- b. Subjects who, after enrollment, admit to missing 2 or more injections after the first injection.

C.7.iii Subjects that Withdraw from the Study

If a subject in the RCT withdraws their consent, we will continue to provide the standard dose of 250 mg until treatment can be transitioned to the patient's healthcare provider, if desired, to ensure there is no lapse in patient care. Additional subjects will be recruited to maintain the sample size.

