C.9. Medical monitor and Logistic Coordinating Core

A Medical Monitor has been selected for this trial. The Medical Monitor will receive reports from each clinical center which will be compiled by the NICHD funded **Logistic Coordinating Core (LCC)**. The LCC facilitates and coordinates the OPRC clinical study activities and ensures that all activities are implemented.

The role of the Medical Monitor will include:

- Ongoing monitoring of SAE reports submitted by the clinical centers to identify safety concerns and suggest protocol modifications, if necessary
- Advise IND sponsor, Principal Investigator(s), and DMC regarding SAEs and safety concerns
- Provide reports when necessary to the Principal Investigator and DMC

D. Statistical Analysis and Sample Size Justification

D.1. Primary and Secondary Outcomes

The primary outcome is the rate of preterm birth (delivery prior to 37 0/7 weeks) according to 17-OHPC concentration.

Secondary outcomes include:

- The rate of spontaneous PTB prior to 32 0/7 and 35 0/7 weeks according to the concentration of 17-OHPC.
- The impact of dose, race, BMI and co-medications on plasma 17-OHPC concentrations
- Plasma concentrations of 17-OHPC, mono-hydroxylated metabolite of 17-OHPC
- Concentrations of progesterone and 17-hydroxyprogesterone in maternal and cord blood according to the weekly dose of 17-OHPC
- The frequency of maternal side effects according to dose and plasma concentration
- The frequency of neonatal complications according to dose and plasma concentration
- Impact of dose on rates of spontaneous PTB
- The correlation of progesterone and 17-hydroxyprogesterone in maternal plasma and whole blood to pharmacological and clinical outcomes

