Based on the simulated distribution of 17-OHPC plasma concentration at higher doses in this study, we expect the variance of log-transformed concentration to be 0.226. Given the results of the prior study, we have estimated the hazard ratio corresponding to a one-unit increase in log-transformed 17-OHPC concentration to be 0.49. We also anticipate that 28% of study participants will deliver preterm. Thus, a Cox regression based on a sample of 208 women will have 80% power at the $\alpha=0.05$ significance level to detect a hazard ratio of 0.49. This sample size will be adjusted for the presence of other covariates in the Cox model; assuming that additional covariates such as BMI account for 30% of the variation in log-transformed plasma concentration, we require a sample size of **296 women** to achieve 80% power (Table 1). Our

published data indicate that only maternal BMI affects plasma concentrations of 17-OHPC and accounts for no more than 30% of the variation in plasma concentrations (Figure 7). We will recruit 300 subjects overall to account for non-compliance or non-collection of plasma for analysis of 17-OHPC. Data from non-compliant subjects will not be used for any analysis related to plasma 17-OHPC concentration. In addition, data analysis related to plasma 17-OHPC concentration in those subjects who stop 17-OHPC treatment because of a drug allergy, thrombosis or cholestatic jaundice will not be utilized, but their outcomes will be kept and included in the secondary outcomes that are not related to plasma 17-OHPC concentrations. The sample size will be sufficient to address secondary outcomes since the variation in the variables studied will be far smaller than the variation in plasma 17-OHPC concentration.

All three centers have recruited very well in other studies of 17-OHPC from the MFMU. The pool of subjects annually available for recruitment will exceed 300. Even at a study acceptance rate as low as 30%, there are more than enough subjects to enable us to reach our recruitment goal. We anticipate an acceptance rate closer to 50%. All power analyses were performed using PASS 13. [CITE: PASS 13 Power Analysis and Sample Size Software (2014). NCSS, LLC. Kaysville, Utah, USA, ncss.com/software/pass.]

Table 1. Total Sample Size Required for 80% Power

		% variation accounted for by additional covariates			
		0%	10%	20%	30%
% participants delivering preterm	26%	223	248	279	319
	27%	215	239	269	307
	28%	208	231	259	296
	29%	200	223	250	286

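### The stop-treatment exclusion has no exception for samples drawn before the event, so the listed treatment-stopping events cannot be related to 17-OHPC concentration

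*Combined protocol and SAP*

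**What the plan says.** **The planned analysis.** Research question 2 in C.2 asks: "Are maternal side effects increased at higher doses or higher plasma concentrations of 17-OHPC". D.1 lists the matching secondary outcome: "The frequency of maternal side effects according to dose and plasma concentration".

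**The exclusion in C.7.i.** When treatment is stopped, "the subject will be retained in the study but their data related to 17-OHPC concentration will not be utilized since they will have stopped". The reason and the replacement rule follow: "since they will have stopped the medication. Additional subjects will be recruited to maintain the sample size". Scenario (a) covers "Systemic drug allergy, thrombosis during pregnancy, cholestatic jaundice, suicidal ideation, or other concern" about safety; scenario (b) is an unplanned pregnancy termination.

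**The exclusion in D.2.** Concentration analysis "in those subjects who stop 17-OHPC treatment because of a drug allergy, thrombosis or cholestatic jaundice will not be utilized". This list has three reasons. Suicidal ideation, other safety concerns and termination are not on it. On what remains usable for these women, the same section adds: "their outcomes will be kept and included in the secondary outcomes that are not related to plasma 17-OHPC concentrations".

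**Sampling.** C.6.v schedules RCT maternal blood before the second injection (ideally day 7), at 26-30 weeks after at least seven injections, 6-9 weeks after that, and at delivery. Under C.5 treatment runs to 36 6/7 weeks.

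**Neighbouring rules.** C.2 does not use ancillary-cohort data for question 2. C.7.ii withholds the concentration data of non-compliant women from the primary outcome only, whereas D.2 withholds them from all concentration analyses.

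**The concern.** For the listed events, the outcome under study is also the ground for exclusion. A woman with a thrombosis in week 33 may have a valid steady-state trough from week 28, yet she leaves the side-effect-by-concentration analysis because she had the thrombosis. Replacement recruitment refills the set with women who did not have the event. The reason given, that she is no longer on the drug, is sound for samples drawn after the stop. It does not apply to a sample drawn while she was still being treated.

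At stake is the concentration half of question 2 for events serious enough to stop treatment. C.8 itself raises the possibility that thrombosis risk increases with dose, and B.4 stresses how widely concentrations vary at a fixed dose, so the dose comparison does not fully stand in for the concentration analysis.

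**Working it through.** The plan gives no figure on this point to reproduce. The core of the check is textual; the arithmetic only sizes it.

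**1. Text side by side**

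- Side effects by plasma concentration is a concentration-related secondary outcome (D.1).
- D.2 keeps these women's outcomes only for secondary outcomes that are not related to concentration, so they drop out of that analysis.
- C.7.i words the exclusion per subject, not per sample.
- The methods text in D.1 covers secondary outcomes that are survival or continuous variables. It says nothing on side effects by concentration that would restore these women.
- Result: the analysis contains no event of a listed type that led to stopping, whatever the true relation.

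**2. How many thrombosis cases could have an earlier 26-30 week trough**

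Inputs:
- C.8 expects no more than 3 thromboses in the 250 mg group. It calls this 3% but gives the group as 150: 3/150 = 2%. A 2:1 split of 300 puts 100 women on 250 mg: 3/100 = 3%. Range used: 2% to 3%, as a ceiling.
- Assumed: the same risk in both arms, a constant event rate over treatment, and treatment to 36 6/7 (36.86) weeks.

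Events: 300 × 0.02 = 6 to 300 × 0.03 = 9.

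Share of treatment time after the draw = (36.86 − draw) / (36.86 − start), with the draw at 26-30 weeks and at least 7 weeks after the start:
- lowest (start 16, draw 30): 6.86/20.86 = 0.329
- highest (start 19, draw 26): 10.86/17.86 = 0.608

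Cases with an earlier trough: 6 × 0.329 = 1.97 to 9 × 0.608 = 5.47, so about 2 to 5.

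Sensitivity:
- If the 28% expected to deliver preterm all did so just after the draw (extreme), the lowest share is 0.72 × 6.86 / (14 + 0.72 × 6.86) = 0.261, giving 6 × 0.261 = 1.6 cases.
- If the risk at 500 mg were twice that at 250 mg (hypothetical), events would be p × (100 + 200 × 2) = 10 to 15, of which 10 × 0.329 = 3.3 to 15 × 0.608 = 9.1 would have the trough.
- If the true risk lies below the ceiling, there could be one such case or none.

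**3. Precision of a case/non-case concentration ratio**

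D.2 states "we expect the variance of log-transformed concentration to be 0.226", so SD = √0.226 = 0.475. With k cases and about 290 non-cases (assumed), SE = 0.475 × √(1/k + 1/290).
- k = 2: SE = 0.337; exp(1.96 × 0.337) = 1.94
- k = 5: SE = 0.214; exp(1.96 × 0.214) = 1.52

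The 95% interval is therefore the estimate multiplied or divided by about 1.9 (2 cases) to 1.5 (5 cases).

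Caveat on the variance: in the usual two-sided Cox formula, 7.849 / (0.226 × 0.509 × 0.28) = 244, not D.2's 208. A variance of 0.266 reproduces Table 1, though the documents do not confirm that value. With 0.266 the factors become 2.05 and 1.58, so the conclusion is the same.

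**4. Why sampling occasions should not be mixed**

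B.4 gives a half-life of 16.2 ± 6 days. Assuming first-order accumulation, the fraction of steady state after t days is 1 − 2^(−t/h).

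| Half-life (days) | Day 7 | Day 49 | Log difference |
|---|---|---|---|
| 10.2 | 0.38 | 0.96 | 0.93 |
| 16.2 | 0.26 | 0.88 | 1.22 |
| 22.2 | 0.20 | 0.78 | 1.38 |

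The occasion alone shifts the log concentration by more than doubling the dose would (ln 2 = 0.69).

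**The case against.** The best case for leaving the text alone has four parts.

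*These events may not be the side effects meant.* Side effects are asked about at the weekly contacts, serious adverse events have their own reporting path (C.6.iii), and thrombosis has its own review in C.8. The documents do not define maternal side effects. This stands, and the point is conditional on counting the events among them.

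*The events are not lost.* The by-dose comparison is randomised and keeps them, as does DMC review. This also stands. A reader might infer that the plan hides these events, or might read their absence from the concentration set as a low incidence. Neither is supported, because D.2 expressly keeps the outcomes for analyses that do not involve concentration. What those analyses do not supply is the concentration half of question 2.

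*Too few cases to matter.* C.8's figure is an upper expectation, and C.3.i excludes women with current or past thrombosis. Largely accepted: the result can only be descriptive.

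*Only later samples, or only the primary analysis, are meant.* The stated reason suggests the former, but the rule is not written that way. As to the latter, C.7.ii limits its own exclusion to the primary outcome, C.7.i has no such limit, and D.2 speaks of secondary outcomes.

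A reader might also infer that all side effects that end treatment are removed. The lists do not go that far. A woman who stops by her own choice, for example over injection discomfort, is not clearly under C.7.i and would more likely fall under the non-compliance rule, on whose scope C.7.ii and D.2 disagree.

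**Conclusion.** The point holds in a limited form. As written, C.7.i and D.2 remove women whose treatment was stopped for the listed safety reasons from all concentration-related analyses, including those with a valid earlier sample. If the events count as maternal side effects, their relation to concentration is not estimable in the analysis planned under question 2 and D.1.

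A reader might go further and say that the analysis is biased toward no relation. For the excluded event types there is nothing left to bias. For a pooled any-side-effect analysis, that direction follows only if the cases had higher concentrations. The documents do not show this; C.8 calls a higher thrombosis risk at higher doses only a possibility.

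The effect is small: on the ceiling and equal-risk assumptions, at most about 2 to 5 thromboses with an earlier trough, possibly none or one. The documents give no expected rates for allergy or cholestatic jaundice. Side effects that do not stop treatment stay in the analysis. This is a cheap clarification of a planned safety question.

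**What to change.** - Leave the exclusion as it is for the primary preterm-birth analysis.
- In C.7.i and in D.2, add that for the safety-by-concentration analyses only, RCT women who stopped treatment are kept, using samples drawn on treatment before the event; only samples drawn after the stop are excluded.
- Compare cases with non-cases at the same sampling occasion: pre-second-injection with pre-second-injection, 26-30 weeks with 26-30 weeks.
- Report the number of cases at each occasion and label the result descriptive.
- State whether the listed stopping events count as maternal side effects.
- Reconcile the stopping reasons in C.7.i with those in D.2, and the scope of the non-compliance exclusion in C.7.ii with that in D.2.

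Cost: one sentence in each of C.7.i and D.2, a short paragraph on matching by occasion, and the reconciled wording. No new samples are needed. The downside is slightly more analysis work for a descriptive result.

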The primary outcome will be the rate of preterm birth (<37 weeks) according to the plasma concentration of 17-OHPC (as a continuous variable) from the 26-30 week sample. The distribution of plasma concentration is expected to be highly positively skewed; thus, a natural logarithmic transformation will be applied to plasma concentrations to produce normally distributed values. A Cox proportional hazard model will be employed to analyze the effect of continuous log-transformed plasma concentration on event-free survival (in this case, “event-free survival” meaning “not birthed until term”). Specifically, the hazard of delivering preterm will be modeled as a function of log-transformed plasma concentration and additional covariates that may influence treatment effectiveness (e.g., BMI, race, gestational age at study entry). Adjusted survival curves will be calculated using the relationship between the hazard function and the survival function. A Wald test will be performed to determine whether the hazard ratio corresponding to a one-unit increase in log-transformed plasma concentration is significantly different from zero. Wald and likelihood ratio tests will also be employed to test for the significance of additional covariates, and stratified analyses may be considered if appropriate (i.e., race-specific analyses). This semi-parametric modeling approach will allow us to analyze the effect of, and not just the presence of, covariates on event-free survival in a robust manner.

Secondary outcomes that are also survival outcomes (such as spontaneous PTB, spontaneous PTB before 32 weeks and before 35 weeks, and indicated PTB) will be analyzed in a similar fashion to the primary outcome analysis described above. For other secondary outcome measures that are continuous variables (maternal and infant hospital days, maternal and fetal plasma concentrations of progesterone, hydroxyprogesterone, 17-OHPC and its metabolite, etc.), linear regression models with appropriate covariates will be utilized.

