We will also compare preterm birth rates between treatment groups (250 or 500 mg). Descriptive statistics will be generated for key characteristics of the treatment groups at baseline. For continuous variables, we will report means and standard deviations or medians and interquartile ranges (the latter in the case of skewed distributions or large outliers). Counts and percentages will be reported for categorical variables. We will then construct a Cox model and produce adjusted survival curves to assess the magnitude of differences in PTB rate

between groups while adjusting for covariates that may influence treatment effectiveness (e.g., BMI, race, gestational age at study entry).

We have previously performed population pharmacokinetic analysis of 17-OHPC in twin and singleton pregnancies. In this study, we will also use population pharmacokinetic analysis to evaluate the contribution of various covariates to the observed variability in the trough plasma concentrations of 17-OHPC, a surrogate measure of drug exposure.

D.2. Sample Size and Power

A Cox proportional hazards regression model will be used to assess the effect of log-transformed 17-OHPC concentration on event-free survival, while adjusting for covariates such as maternal BMI.

The recruited cohort of women will be sufficiently large to provide a wide range of drug exposures and enable evaluation of several potential covariates on plasma concentration of 17-OHPC and to describe the association between plasma concentration of 17-OHPC and its efficacy. Based on the large variation in 17-OHPC concentrations we have reported in clinical trials with the standard dose, we are confident that the range of concentrations of 17- OHPC that will be achieved with the two doses selected will provide a sufficiently wide range (between 4 and 112 ng/ml) to enable the performance of a robust concentration response assessment (Figure 7). Based on these simulated data, we estimate that 99% of subjects will achieve a concentration > 10 ng/ml with the 500 mg/week dose.

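### D.2 calls the sample sufficient for all secondary outcomes, but its reason does not cover the Cox-analysed preterm-birth outcomes, and power for any preterm birth by dose is below 80%

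*Combined protocol and SAP*

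**What the plan says.** D.2 sizes the trial for one analysis: the Cox regression of PTB before 37 weeks on log-transformed plasma concentration. Its sizing effect is explicit: "we have estimated the hazard ratio corresponding to a one-unit increase in log-transformed 17-OHPC concentration to be 0.49". So is its event rate: "We also anticipate that 28% of study participants will deliver preterm".

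D.2 then turns to everything else in one sentence: "The sample size will be sufficient to address secondary outcomes since the variation in the variables studied will be far smaller". The yardstick is plasma concentration. D.2 gives no power, detectable effect or event count for any secondary outcome, and no limit on which outcomes are meant.

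D.1 lists among the secondary outcomes "The rate of spontaneous PTB prior to 32 0/7 and 35 0/7 weeks according to the concentration of 17-OHPC" and "Impact of dose on rates of spontaneous PTB". It assigns the primary outcome's Cox method to a group of them: "Secondary outcomes that are also survival outcomes (such as spontaneous PTB, spontaneous PTB before 32 weeks and before 35 weeks, and indicated PTB"). It also plans a dose comparison of any PTB: "We will also compare preterm birth rates between treatment groups (250 or 500 mg"). That comparison uses a Cox model whose stated purpose is to "produce adjusted survival curves to assess the magnitude of differences in PTB rate" between the groups.

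**The concern.** The reason offered belongs to continuous outcomes. In a linear regression, a less variable outcome gives a smaller standard error, so the sentence may well be true for hormone concentrations or hospital days. A Cox model for time to preterm delivery has no such residual variance. Its information comes from the number of events, the size of the effect and the spread of the predictor.

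For the dose comparison, less spread works against the trial. Dose enters as a 2:1 binary variable. On the plan's medians its variance in log-concentration units is 2/9 × (ln 2)² = 0.107, against 0.226 assumed for concentration itself.

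Whether 500 mg lowers PTB relative to 250 mg is the trial's only randomised contrast. If D.2 says the sample is sufficient for it, a reader may take a non-significant result as evidence that the doses do not differ.

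**Working it through.** **The plan's own figures.** D.2 gives no power figure for a secondary outcome, so there is none to reproduce. Its only sample sizes, 208 and 296, are for the primary analysis. The usual formula is events = (z_α + z_β)² / (variance × (ln HR)²), and N = events / 0.28, divided by 0.70 for the covariates.
- Two-sided: 68.2 events, N = 244 and 348.
- One-sided: 53.8 events, N = 192 and 274.

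Neither matches 208 and 296. That is a separate matter, and none of the main results below uses those sample sizes or the variance of 0.226.

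**Inputs for any PTB by dose.**
- HR 0.49 per natural-log unit, and 28% PTB (D.2).
- Expected medians of 10 ng/ml on 250 mg and 20 ng/ml on 500 mg (B.5).
- 300 women randomised 2:1 to 500 mg and 250 mg (C.2), so about 200 and 100.
- α = 0.05. D.2 does not state sidedness, so both are shown.

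**Implied dose effect.** HR = 0.49^ln(20/10) = 0.49^0.693 = 0.610; |ln HR| = 0.494.

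**Power (Schoenfeld).** Power = Φ(√(events × 2/9) × 0.494 − z), with z = 1.960 two-sided or 1.645 one-sided.

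(a) *D.2's event rate.* 300 × 0.28 = 84 events. Under proportional hazards this means about 36.1% on 250 mg and 23.9% on 500 mg. √(84 × 2/9) × 0.494 = 2.136. Power is 57.0% two-sided and 68.8% one-sided.

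(b) *A 250 mg rate taken from B.5.* Half the women there were above 10 ng/ml with 25% PTB, and the rest had 37%: 0.5 × 37% + 0.5 × 25% = 31%. The 500 mg rate is 1 − 0.69^0.610 = 20.3%. Events are 31 + 40.5 = 71.5, which is 23.8% overall. √(71.5 × 2/9) × 0.494 = 1.971. Power is 50.4% two-sided and 62.8% one-sided.

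**Other methods.** Schoenfeld's approximation runs a little low when the larger arm has the lower risk.

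| Method | (a) 84 events | (b) 71.5 events |
|---|---|---|
| Schoenfeld, two-sided | 57% | 50% |
| Log-rank simulation, two-sided | 62% | 55% |
| Log-rank simulation, one-sided | 73% | 66% |
| Freedman, two-sided | 62% | – |
| Two proportions, two-sided | 60% | – |
| Fisher, two-sided | 58% | – |

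The simulation uses exponential times, 100 and 200 women, and a common cut-off. Letting concentration vary within arms leaves (a) at 60–62%. Rescaling so that the plan's 208 gives exactly 80% two-sided power in the primary analysis puts (a) at about 64%.

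**Distance from 80%.** Two-sided, (1.960 + 0.842)² / (2/9 × 0.494²) ≈ 144 events are needed, or about 516 women at 28% PTB. One-sided, it is about 114 events or 406 women.

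**Precision.** With standard error 1/√(events × 2/9), the expected 95% interval around 0.61 is 0.39 to 0.96 at 84 events and 0.37 to 1.00 at 71.5.

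**Spontaneous and early PTB.** These are subsets of any PTB, so they cannot have more events. At the same hazard ratio and number of women, power is no higher. The documents give no event rates for them, so no figure is given here.

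**The case against.** **Secondary outcomes need not have 80% power, and to address an outcome may only mean to estimate it.** Both points are fair. D.1 does describe the dose model as assessing the size of differences. But the sentence stands in the section on sample size and power, follows an 80% power claim, and gives a reason that fails for these outcomes. If estimation is meant, D.2 should say so.

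**Any PTB by dose is not in D.1's bulleted list.** This is correct: the list has spontaneous PTB by dose, and any PTB by dose appears in the analysis text. The computed figure therefore describes a planned analysis and serves only as a ceiling, at the same hazard ratio, for the listed outcome. A stronger effect on spontaneous PTB would offset part of the loss.

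**More women may contribute.** C.7 allows replacement. An assumed 330–360 randomised women would give 61–65% two-sided by Schoenfeld at 28% PTB. C.5 says ancillary women are not randomised, and the text does not say whether they enter the dose comparison. If an assumed 50–150 of them joined the 250 mg group, Schoenfeld gives about 70–82% in (a), but the comparison would no longer be randomised. The figures here are for randomised women only.

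**Stronger readings that the documents do not support.**
- A reader might infer that the trial is too small or must enrol more. D.2 does not promise 80% power for any secondary outcome, and nothing requires it.
- A reader might infer an arithmetic error. D.2 prints no secondary power figure that could be miscalculated.
- A reader might take 50–57% as the power. That reflects one approximation, and its lower end departs from D.2's 28%.
- A reader might assume a plateau above 10 ng/ml and conclude that power is far lower. B.5 argues against a plateau, and it is not the sizing model.
- A reader might infer that the sponsor will read a null result as no effect. No passage says so.

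**Conclusion.** The sufficiency sentence is unsupported for the Cox-analysed outcomes: spontaneous PTB, spontaneous PTB before 35 and 32 weeks, indicated PTB, and PTB by dose. For any PTB by dose in 300 randomised women, no method tried reaches 80%. Two-sided power is about 57–62% at D.2's event rate (69–73% one-sided) and about 50–55% with the B.5-derived 31% rate on 250 mg. These figures rest on the plan's hazard ratio carrying over to dose through a doubling of median concentration, and on proportional hazards. For the spontaneous and early outcomes the conclusion is qualitative only.

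The severity is minor. The sentence changes no analysis, sample size or decision rule. It overstates what the design can show.

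**What to change.** In D.2:
- Limit the sufficiency sentence to continuous outcomes analysed by linear regression, or delete it.
- State that the sample was not set for the PTB secondary outcomes or the dose comparison.
- State that power for any PTB by dose among randomised women is below 80%, roughly 50–62% two-sided depending on method and event rate, and name the assumptions.
- State that these analyses will be reported as estimates with 95% confidence intervals, which matches the purpose D.1 already gives the dose model.

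This is a wording change. It adds no patients, visits or analyses. Its only cost is a less favourable stated property of the design.
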